3.2.1.8 Creatinine Clearance

The estimated Creatinine Clearance will be calculated using Cockcroft-Gault equation as follows:

$$C_{Cr} = \left\{ \frac{(140 - \text{age}) \times \text{weight}}{72 \times S_{Cr}} \right\} \text{ Multiply by } 0.85 \text{ (if patient is female)}$$

C_{Cr} (creatinine clearance) = mL/minute

Age = years

Weight = kg (the last weight measured closest to the time when serum creatinine is measured)

S_{Cr} (serum creatinine) = mg/dL.

Creatinine clearance will be summarised and listed by cohort, by visit.

3.2.1.9 Plasma 4 β -hydroxy cholesterol

For the core module only, individual 4 β -hydroxy cholesterol concentration data by cohort, by visit will be listed.

3.2.1.10 Physical Examination

A complete physical examination will be performed at visits specified in schedule of assessments for each module; baseline height, weight, body mass index (BMI) and BMI category (< 18.5, 18.5 - < 25, 25 - < 30, \geq 30) will be summarised. All physical examination findings will be listed as well.

All abnormal findings from the physical exam will be summarised and reported under AEs.

3.2.1.11 ECG

All ECG data received will be presented in data listings.

Absolute values, changes from baseline and percentage change from baseline to each scheduled visit will be summarised by module, by part, by cohort and visit for the following ECG variables: heart rate, QT interval corrected for heart rate using Fridericia's formula (QTcF), RR, PR, QRS, and QT. The average of the three individual tracings will be used in summaries. However, the individual tracings will be displayed in the data listings.

Number and percentage of patients with QTcF results in each of the following categories will be summarised:

- greater than AstraZeneca Cardiac SKG upper reference range at any time on treatment.
- absolute value > 450 msec.
- absolute value > 480 msec.
- absolute value > 500 msec.
- change from baseline > 30 msec.
- change from baseline > 60 msec.
- absolute value > 450 msec and change from baseline > 30 msec.
- absolute value > 500 msec and change from baseline > 60 msec.

3.2.1.12 Echocardiogram

left ventricular ejection fraction (LVEF) is collected for all patients in combination module 1. Change of LVEF from baseline will be calculated at each scheduled post-baseline assessment time and summarised by part, by cohort and visit..

The absolute change from baseline will also be summarised by following categories:

- Any increase
- No change
- Any decrease
- 0 to <10% decrease
- 10 to <20% decrease
- $\geq 20\%$ decrease
- $\geq 10\%$ decrease and \geq Lower Limit Normal (LLN)

- $\geq 10\%$ decrease and $< LLN$
- $\geq 20\%$ decrease and $\geq LLN$
- $\geq 20\%$ decrease and $< LLN$

3.2.1.13 Eastern Cooperative Oncology Group performance status (ECOG PS)

ECOG PS status will be summarised and listed by grade (0-4) for each visit.

3.2.2 Secondary Outcome Variables

3.2.2.1 Calculation or derivation of tumour response variables

3.2.2.1.1 RECIST visit responses

For all patients, the RECIST tumour response data will be used to determine each patient's visit response according to RECIST version 1.1. It will also be used to determine if and when a patient has progressed in accordance with RECIST and also their best objective response to study treatment.

Baseline radiological tumour assessments are to be performed no more than 28 days before the first dose/administration of study medication on cycle 1, day 1 and ideally as close as possible to the start of study treatment. Tumour assessments are then performed every 8 weeks (± 1 week) following start of study treatment on cycle 1, day 1 until confirmed disease progression.

If an unscheduled assessment is performed, and the patient has not progressed, every attempt should be made to perform the subsequent assessments at their scheduled visits. This schedule is to be followed in order to minimise any unintentional bias caused by some patients being assessed at a different frequency than other patients.

From the investigator's review of the imaging scans, the RECIST tumour response data will be used to determine each patient's visit response according to RECIST version 1.1. At each visit, patients will be programmatically assigned a RECIST 1.1 visit response of complete response (CR), partial response (PR), stable disease (SD) or partial disease (PD) (see [Table](#)), using the information from target lesions (TLs), non-target lesions (NTLs) and new lesions and depending on the status of their disease compared with baseline and previous assessments. If a patient has had a tumour assessment which cannot be evaluated, then the patient will be assigned a visit response of not evaluable (NE) (unless there is evidence of progression in which case the response will be assigned as PD).

RECIST outcomes (i.e. PFS, ORR etc.) will be calculated programmatically for the site investigator data from the overall visit responses.

In addition, the objective tumour response assessment will also be assessed for exploratory analysis on a modified RECIST 1.1 criteria considering progression only when confirmed. If progression is not confirmed, then the overall visit response as per modified RECIST should be assessed as SD/ PR or CR and the patient should continue scheduled RECIST 1.1. CT/MRI scans. If progression is confirmed the overall visit response should be assessed as progressive disease as per modified RECIST.

Target lesions (TLs)

Measurable disease is defined as having at least one measurable lesion, not previously irradiated, which is ≥ 10 mm in the longest diameter (LD) (except lymph nodes which must have short axis ≥ 15 mm) with computed tomography (CT) or magnetic resonance imaging (MRI) and which is suitable for accurate repeated measurements. A patient can have a maximum of 5 measurable lesions recorded at baseline with a maximum of 2 lesions per organ (representative of all lesions involved and suitable for accurate repeated measurement) and these are referred to as target lesions (TLs). If more than one baseline scan is recorded, measurements from the one that is closest and prior to first dose/administration of study medication will be used to define the baseline sum of TLs. It may be the case that, on occasion, the largest lesion does not lend itself to reproducible measurement in which circumstance the next largest lesion, which can be measured reproducibly, should be selected.

All other lesions (or sites of disease) not recorded as TL should be identified as NTLs at baseline. Measurements are not required for these lesions, but their status should be followed at subsequent visits.

Note: For patients who do not have measurable disease at entry (i.e. no TLs) but have non-measurable disease, evaluation of overall visit responses will be based on the overall NTL assessment and the absence/presence of new lesions. If a patient does not have measurable disease at baseline, then the TL visit response will be not applicable (NA).

Table 7: TL visit responses

Visit Responses	Description
Complete Response (CR)	Disappearance of all TLs. Any pathological lymph nodes selected as TLs must have a reduction in short axis to <10mm.

Visit Responses	Description
Partial response (PR)	At least a 30% decrease in the sum of diameters of TLs, taking as reference the baseline sum of diameters, as long as criteria for PD are not met.
Progressive disease (PD)	A $\geq 20\%$ increase in the sum of diameters of TLs and an absolute increase of $\geq 5\text{mm}$, taking as reference the smallest sum of diameters since treatment started including the baseline sum of diameters.
Stable disease (SD)	Neither sufficient shrinkage to qualify for PR nor sufficient increase to qualify for PD
Not Evaluable (NE)	Only relevant in certain situations (i.e. if any of the target lesions were not assessed or not evaluable or had a lesion intervention at this visit; and scaling up could not be performed for lesions with interventions). Note: If the sum of diameters meets the progressive disease criteria, progressive disease overrides not evaluable as a target lesion response
Not applicable (NA)	No TLs are recorded at baseline

Rounding of TL data

For calculation of PD and PR for TLs percentage changes from baseline and previous minimum should be rounded to 1 d.p. before assigning a TL response. For example, 19.95% should be rounded to 20.0% but 19.94% should be rounded to 19.9%.

Missing TL data

If all TL measurements are missing then the TL visit response is not evaluable (NE). Overall visit response will also be NE, unless there is a progression of non-TLs or new lesions, in which case the response will be PD.

Scaling

If $> 1/3$ of TL measurements are missing then TL response will be NE, unless the sum of diameters of non-missing TL would result in PD (i.e. if using a value of 0 for missing lesions, the sum of diameters has still increased by 20% or more compared to nadir and the sum of TLs has increased by ≥ 5 mm from nadir).

If $\leq 1/3$ of the TL measurements are missing then the results will be scaled up (based on the sizes at the nadir visit) to give an estimated sum of diameters and this will be used in calculations; this is equivalent to comparing the visit sum of diameters of the non-missing lesions to the nadir sum of diameters excluding the lesions with missing measurements.

Example of scaling

Lesion 5 is missing at the follow-up visit; it had a BL measure of 29.3cm. The sum of lesions 1-4 at the follow-up is 26 cm. The sum of the corresponding lesions at nadir visit is 26.8 cm.

Scale up as follows to give an estimated TL sum of 28.4cm:

$$\frac{26}{26.8} \times 29.3 = 28.4 \text{ cm}$$

CR will not be allowed as a TL response for visits where there is missing data. Only PR, SD or PD (or NE) could be assigned as the TL visit response in these cases. However, for visits with $\leq 1/3$ lesion assessments not recorded, the scaled up sum of TLs diameters will be included when defining the nadir value for the assessment of progression.

Lymph nodes

For lymph nodes, if the size reduces to < 10 mm then these are considered non-pathological. However, a size will still be given and this size should still be used to determine the TL visit response as normal. In the special case where all lymph nodes are < 10 mm and all other TLs are 0mm then although the sum may be > 0 mm the calculation of TL response should be over-written as a CR.

TL visit responses subsequent to CR

A CR can only be followed by CR, PD or NE. If a CR has occurred, then the following rules at the subsequent visits must be applied:

- Step 1: If all lesions meet the CR criteria (i.e. 0mm or < 10mm for lymph nodes) then response will be set to CR irrespective of whether the criteria for PD of TL is also met i.e. if the sum of diameters for lymph node short axis increases by 20% but all lymph node TL remain < 10mm.
- Step 2: If some lesion measurements are missing but all other lesions meet the CR criteria (i.e. 0mm or < 10mm for lymph nodes) then response will be set to NE irrespective of whether, when referencing the sum of TL diameters, the criteria for PD are also met.
- Step 3: If not all lesions meet the CR criteria (i.e., a pathological lymph node is selected as TL has short axis ≥ 10 mm or the reappearance of previously disappeared lesion) or a new lesion appears, then response will be set to PD.
- Step 4: If after steps 1 – 3 a response can still not be determined the response will be set to remain as CR

TL too big to measure

If a TL becomes too big to measure this should be indicated in the database and a size ('x') above which it cannot be accurately measured should be recorded. If using a value of x in the calculation of TL response would not give an overall visit response of PD, then this will be flagged and reviewed by the study team, if appropriate blinded to treatment assignment. It is expected that a visit response of PD will remain in the vast majority of cases.

TL too small to measure

If a TL becomes too small to measure, then this will be indicated as such on the case report form and a value of 5mm will be entered into the database and used in TL calculations. However, a smaller value may be used if the radiologist has not indicated 'too small to measure' on the case report form and has entered a smaller value that can be reliably measured. If a TL response of PD results, then this will be reviewed by the study team.

Irradiated lesions/lesion intervention

Previously irradiated lesions (i.e. lesion irradiated prior to entry into the study) should be recorded as NTLs and should not form part of the TL assessment.

Any TL (including lymph nodes), which has had intervention during the study (for example, irradiation / palliative surgery / embolisation), should be handled in the following way and once a lesion has had

intervention then it should be treated as having intervention for the remainder of the study noting that an intervention will most likely shrink the size of tumours:

- Step 1: the diameters of the TLs (including the lesions that have had intervention) will be summed and the calculation will be performed in the usual manner. If the visit response is PD this will remain as a valid response category.
- Step 2: If there was no evidence of progression after step 1, treat the lesion diameter (for those lesions with intervention) as missing and if $\leq 1/3$ of the TLs have missing measurements then scale up as described in the ‘Scaling’ section below. If the scaling results in a visit response of PD then the patient would be assigned a TL response of PD.
- Step 3: If, after both steps, PD has not been assigned, then, if appropriate (i.e. if $\leq 1/3$ of the TLs have missing measurements), the scaled sum of diameters calculated in step 2 should be used, and PR or SD then assigned as the visit response. Patients with intervention are evaluable for CR as long as all non-intervened lesions are 0 (or < 10 mm for lymph nodes) and the lesions that have been subject to intervention have a value of 0 (or < 10 mm for lymph nodes) recorded. If scaling up is not appropriate due to too few non-missing measurements, the visit response will be set as NE.

At subsequent visits the above steps will be repeated to determine the TL and overall visit response. When calculating the previous minimum, lesions with intervention should be treated as missing and scaled up (as per step 2 above).

Lesions that split in two

If a TL splits in two, then the LDs of the split lesions should be summed and reported as the LD for the lesion that split.

Lesions that merge

If two TLs merge, then the LD of the merged lesion should be recorded for one of the TL sizes and the other TL size should be recorded as 0cm.

Change in method of assessment of TLs

CT, MRI and clinical examination are the only methods of assessment that can be used within a trial, with CT and MRI being the preferred methods and clinical examination only used in special cases. If a

change in method of assessment occurs between CT and MRI this will be considered acceptable and no adjustment within the programming is needed.

If a change in method involves clinical examination (e.g. CT changes to clinical examination or vice versa), any affected lesions should be treated as missing. The TL visit response may still be evaluable if the number of missing TL measurements at a visit is $\leq 1/3$ of the total number of TLs.

Non-Target Lesions (NTLs) and new lesions – site investigator data

At each visit, the investigator should record an overall assessment of the NTL response. This section provides the definitions of the criteria used to determine and record overall response for NTL at the investigational site at each visit.

NTL response will be derived based on the Investigator's overall assessment of NTLs as described in [Table 2](#).

To achieve 'unequivocal progression' on the basis of NTLs, there must be an overall level of substantial worsening in non-target disease such that, even in the presence of SD or PR in TLs, the overall tumour burden has increased sufficiently to merit a determination of disease progression. A modest 'increase' in the size of one or more NTLs is usually not sufficient to qualify for unequivocal progression status.

Details of any new lesions will also be recorded with the date of assessment. The presence of one or more new lesions is assessed as progression.

A lesion identified at a follow up assessment in an anatomical location that was not scanned at baseline is considered a new lesion and will indicate disease progression.

The finding of a new lesion should be unequivocal: i.e. not attributable to differences in scanning technique, change in imaging modality or findings thought to represent something other than tumour.

New lesions will be identified via a Yes/No tick box. The absence and presence of new lesions at each visit should be listed alongside the TL and NTL visit responses.

A new lesion indicates progression so the overall visit response will be PD irrespective of the TL and NTL response.

If the question 'Any new lesions since baseline' has not been answered with Yes or No and the new lesion details are blank this is not evidence that no new lesions are present but should not overly affect the derivation. This scenario (i.e. whereby new lesion response is NE), should only occur in exceptional cases, as missing data for the new lesion field should always be queried.

Symptomatic progression is not a descriptor for progression of NTLs: it is a reason for stopping study therapy and will not be included in any assessment of NTLs.

Patients with ‘symptomatic progression’ requiring discontinuation of treatment without objective evidence of disease progression at that time should continue to undergo tumour assessments where possible until objective disease progression is observed.

Table 8: NTL Visit Responses

Visit Responses	Description
Complete Response (CR)	Disappearance of all NTLs present at baseline with all lymph nodes non-pathological in size (<10 mm short axis).
Progressive Disease (PD)	Unequivocal progression of existing NTLs. Unequivocal progression may be due to an important progression in one lesion only or in several lesions. In all cases the progression MUST be clinically significant for the physician to consider changing (or stopping) therapy.
Non-CR/Non-PD	Persistence of one or more NTLs with no evidence of progression.
Not Evaluable (NE)	Only relevant when one or some of the NTLs were not assessed and, in the investigator's opinion, they are not able to provide an evaluable overall NTL assessment at this visit. Note: For patients without TLs at baseline, this is relevant if any of the NTLs were not assessed at this visit and the progression criteria have not been met.

Visit Responses	Description
Not Evaluable (NE)	
Only relevant when one or some of the NTLs were not assessed and, in the investigator's opinion, they are not able to provide an evaluable overall NTL assessment at this visit.
 
Note: For patients without TLs at baseline, this is relevant if any of the NTLs were not assessed at this visit and the progression criteria have not been met.

Not Applicable (NA)	Only relevant if there are no NTLs at baseline

Overall visit response

[Table](#) defines how the previously defined TL and NTL visit responses will be combined with new lesion information to give an overall visit response.

Table 7: Overall visit responses

TARGET	NON-TARGET	NEW LESIONS	OVERALL VISIT RESPONSE
CR	CR or NA	No (or NE)	CR
CR	Non-CR/Non-PD or NE	No (or NE)	PR
PR	Non-PD or NE or NA	No (or NE)	PR
SD	Non-PD or NE or NA	No (or NE)	SD
PD	Any	Any	PD
Any	PD	Any	PD
Any	Any	Yes	PD
NE	Non-PD or NE or NA	No (or NE)	NE
NA	CR	No (or NE)	CR
NA	Non-CR/Non-PD	No (or NE)	SD
NA	NE	No (or NE)	NE

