9.4.1 Efficacy analyses

These are secondary variables.

The efficacy assessment of Part A (dose escalation) will be done using ORR. All efficacy endpoints will be used in Part B (expansions) efficacy assessment.

Tumour Response Data

Data will be summarised for dosed patients with measurable disease at baseline and separately for dosed patients with a baseline tumour assessment, unless otherwise specified.

Data will be listed and summarised by cohort using the following response categories: CR, PR, SD, disease progression and not evaluable (NE).

Waterfall plots (bar charts) indicating the percentage best change from baseline in sum of the diameters of TLs may be produced by cohort.

Tumour response includes the following variables:

- Percentage best change in TL
- Duration of response
- PFS
- ORR

Derivation of tumour response variables

Every 8 weeks (2 cycles), or earlier if disease progression is suspected, patients will be programmatically assigned a RECIST visit response of CR, PR, SD, and disease progression depending on the status of their disease compared to baseline and previous assessments.

Progression of TLs will be calculated in comparison to when the tumour burden was at a minimum (ie, smallest sum of diameters previously recorded during the study). In the absence of progression, tumour response (CR, PR, SD) will be calculated in comparison to the baseline tumour measurements obtained before starting treatment.

If a patient has had a tumour assessment, which cannot be evaluated, then the patient will be assigned a response of NE unless there is evidence of progression in which case the response will be assigned as disease progression.

For TL measurements, if $\frac{1}{3}$ of the TL sizes are missing then a scaling up rule will be applied as follows:

- If ≤ ¼ of lesions recorded at baseline are missing then the results will be scaled up (based on the baseline sizes) to give an estimated sum of diameters and this will be used in calculations (this is equivalent to comparing the visit sum of diameters of the non-missing lesions to the baseline sum of diameters excluding the lesions that are missing and determining at what rate the lesions are changing).

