3.2.2.1.5 Change in target lesion tumour size

The best percentage change in tumour size from baseline will be reported, i.e. the maximum reduction from baseline or the minimum increase from baseline in the absence of a reduction from baseline based on all post baseline assessments.

Tumour size is the sum of the longest diameters (or short axis measurements for lymph nodes) of the target lesions. Target lesions are measurable tumour lesions. Baseline for RECIST is defined to be the

last evaluable assessment prior to starting treatment. The percentage change in target lesion tumour size at each week x for which data are available will be obtained for each patient taking the difference between the sum of the target lesions at each week x and the sum of the target lesions at baseline divided by the sum of the target lesions at baseline multiplied by 100 (i.e. $(\text{week } x - \text{baseline})/\text{baseline} * 100$).

Only patients with measurable disease at baseline will be included in summaries of best percentage change in tumour size.

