4.2.2 Tumour Response

Details of tumour assessment and response will be listed for each patient. This listing will include information on lesion site, the method of assessment, diameter of lesion, sum of diameters of lesions, percent change from baseline, the calculated visit response, non target lesions, new lesions, best objective response, etc.

Best objective response and objective response rate (based on RECIST) will be summarised. For each module/part/cohort/dose, best objective response (BoR) will be summarised by n (%) for each category (CR, PR, SD, PD and NE). The best objective response table will be produced for (a) measurable disease and (b) measurable and non-measurable disease. Clopper-Pearson 80% confidence intervals for the ORR will also be presented in the table.

Target lesion size at each tumour assessment time point will be summarised for the evaluable for objective response set, along with percentage change from baseline (imputation will not be used for this) Also, the best percentage change in tumour size from baseline over all tumour assessment time points will be summarised for the evaluable for objective response set using descriptive statistics (n, mean, standard deviation, median, minimum, maximum).

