Waterfall plots indicating the best percentage change from baseline in sum of the diameters of target lesions will be produced for the evaluable for objective response set. The plot will present each patient's best percentage change from baseline in TL tumour size as a separate bar, with the bars ordered from the largest increase to the largest decrease. A reference line at the -30% change in TL tumour size level, which corresponds with the definition of 'partial' response and another reference line at +20%, corresponds with the definition of 'progressive disease' will be added to the plots. All progressions will be marked with a '●' or designated with patterns or colours for ORR categories. Flagged progressions on the percentage change in TL tumour size at a particular timepoint will be based upon NTL or new lesion progression at that timepoint and flagged progressions on the best percentage change will be based upon NTL or new lesion progression at the same timepoint as the best percentage change. The scale in these plots will be fixed to be from -100 to 100 to avoid presenting extreme values. Values that are capped as a result of this restriction to the scale will be marked with '#'. Values will be ordered in descending order with the imputations due to death appearing first followed by a gap followed by all other patients. Imputed values will be clearly marked with '*' and patients with imputation where there was a death or evidence of progression have different shading to each other and the other patients to make it clear that these are different.

Additionally, ‘spider’ plots will be produced for each treatment group for the evaluable for objective response set. Separate plots should be presented for the absolute value in the sum of target lesions and percentage change in target lesion size over time. These plots depict the sum of target lesion size for each patient or each patient’s percentage change in TL tumour size as a line over time and progression due to non- target and/or new lesions will be indicated. (Imputation will not be used for spider plots.). The scale on y-axis for percentage change plots will be fixed from -100 to +100 to avoid presenting extreme values.

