6 CHANGES OF ANALYSIS FROM PROTOCOL

Some of the PK parameter symbols specified in CSP objective and endpoints been re-defined in SAP section 3.2.2.2 to match with AZ Corporate CSRHLD Reporting Standards version 3.4 (see Table 10)

Table 10: PK parameter symbols re-defined in SAP

Table 10: PK parameter symbols re-defined in SAP

Protocol defined PK symbols	Symbols re-defined in SAP	Parameter definition
AUC	AUC _{inf}	Area under plasma concentration-time curve from zero to infinity (Part A)
AUC _{tau}	AUC _τ	Area under plasma concentration-time curve in the dosing interval τ (τ = 24 for CC1 dose and τ =12 for CC1 dose)
AUC _{0-t}	AUC _{last}	Area under the plasma concentration-curve from zero to the last quantifiable concentration
C _{max,ss}	C _{max}	Maximum observed plasma (peak) drug concentration after multiple dose
C _{min,ss}	C _{min}	Minimum observed plasma concentration after multiple dose
Half-life	t _{1/2λz}	Half-life associated with terminal slope (λ _z) of a semi-logarithmic concentration-time curve, calculated as ln2/λ _z
t _{1/2}	t _{1/2λz}	Half-life associated with terminal slope (λ _z) of a semi-logarithmic concentration-time curve, calculated as ln2/λ _z

Additional PK plasma and urine parameters of interest are elaborated in section 3.2.2.2 of SAP.

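### For missing target lesions the SAP scales on nadir sizes where protocol 9.4.1 scales on baseline sizes, and does not declare it; separately, best percentage change has no cut-off at subsequent therapy.

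*SAP*

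**What the plan says.** **Missing lesions.** Protocol 9.4.1 states that, up to a limited share of missing lesions, "the results will be scaled up (based on the baseline sizes", and explains this as comparing the measured lesions with their own baseline sum. SAP 3.2.2.1.1 (Scaling) states "the results will be scaled up (based on the sizes at the nadir visit", and explains it as a comparison with the nadir sum. The SAP also lets scaled values set later reference points: "the scaled up sum of TLs diameters will be included when defining the nadir value for the assessment of progression".

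**Lesions with an intervention.** The SAP treats these as missing and scales them when the raw sum does not show progression, adding "When calculating the previous minimum, lesions with intervention should be treated as missing and scaled up (as per step 2 above". The scaling text in protocol 9.4.1 covers missing sizes only.

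**A further protocol rule.** Appendix H Table 2 gives a target-lesion response of not evaluable if any target lesion was unassessed, unevaluable or intervened on at the visit, with progression overriding.

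**Declared changes.** SAP Section 6 begins "Some of the PK parameter symbols specified in CSP objective and endpoints been re-defined in SAP section 3.2.2.2" and adds a pointer to further PK parameters. It says nothing on tumour response.

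**Best percentage change.** SAP 3.2.2.1.5 takes the largest reduction, or the smallest increase if there is not "a reduction from baseline based on all post baseline assessments". SAP 4.2.2 repeats that "the best percentage change in tumour size from baseline over all tumour assessment time points will be summarised" and adds "Waterfall plots indicating the best percentage change from baseline in sum of the diameters of target lesions will be produced". None of these names subsequent therapy. Best objective response (SAP 3.2.2.1.2) and response rate (SAP 3.2.2.1.3; protocol 9.4.1) both stop at it.

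**The concern.** The scaled sum decides whether a visit is response, stable disease or progression. Visit responses then feed best objective response, response rate, duration of response and progression-free survival. Each document spells out its own reference, so this is not a loose word. Two programmers, one working from each document, could classify the same scans differently and so confirm or lose an earlier partial response. A reader of the study report would not learn from Section 6 that the rule had changed.

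For best percentage change, the waterfall could show shrinkage achieved on another drug while the response rate beside it excludes that shrinkage.

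**Working it through.** **1. The SAP's own example.** The printed calculation is 26/26.8 × 29.3 = 28.4 cm, which reproduces. The text calls 29.3 cm lesion 5's baseline size. Under the SAP rule the multiplier must be the nadir sum of all five lesions, which would make lesion 5 equal to 29.3 − 26.8 = 2.5 cm at nadir. If 29.3 cm is instead taken as lesion 5's own reference size, the rule gives 26/26.8 × (26.8 + 29.3) = 54.4 cm.

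**2. Formula.** Scaled sum = measured visit sum × (reference sum of all lesions ÷ reference sum of the measured lesions). The reference is baseline in protocol 9.4.1 and nadir in the SAP. Partial response needs at least −30% from baseline; progression needs at least +20% and at least 5 mm from nadir.

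**3. Illustrations.** Sizes are assumed, in mm. Baseline is 30/30/30/30 (sum 120), with one of four lesions missing at the second scan.

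*Missing lesion had shrunk more.* Nadir 20/20/20/8 (sum 68, −43.3%: partial response); visit 22/22/22/missing (measured sum 66).
- Protocol 9.4.1: 66 × 120/90 = 88.0; 88.0/68 − 1 = +29.4%, +20.0 mm: progression, so the earlier response is not confirmed.
- SAP: 66 × 68/60 = 74.8; +10.0% from nadir, −37.7% from baseline: partial response, confirmed.
- Progression starts at 1.2 × 68 = 81.6. That is 81.6 × 90/120 ÷ 3 = 20.4 mm per measured lesion under the protocol and 81.6 × 60/68 ÷ 3 = 24.0 mm under the SAP. The rules conflict between these values.

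*Missing lesion had shrunk less.* Nadir 12/12/12/24 (sum 60, −50.0%: partial response); visit 16/16/16/missing (measured sum 48).
- Protocol 9.4.1: 48 × 120/90 = 64.0; +6.7% from nadir, −46.7% from baseline: partial response.
- SAP: 48 × 60/36 = 80.0; +33.3%, +20.0 mm: progression.
- Progression starts at 1.2 × 60 = 72, so the conflict runs from 72 × 36/60 ÷ 3 = 14.4 mm to 72 × 90/120 ÷ 3 = 18.0 mm.

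*Proportional shrinkage.* Nadir 20/20/20/20; visit 22/22/22/missing. Both rules give 66 × 120/90 = 66 × 80/60 = 88.0, stable disease. They also agree whenever the nadir is the baseline.

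**4. Appendix H Table 2 on the same cases.** The measured sums, 66 and 48, do not exceed the nadirs of 68 and 60, so progression is not met and Table 2 read alone gives not evaluable in both. For intervened lesions Table 2 is the protocol comparator, and the SAP can differ from it at the first post-baseline scan.

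**5. Timing for missing lesions.** At the first post-baseline scan the nadir is the baseline, so the two scaling rules agree. They can part from the second scan, usually 2 × 8 = week 16. Protocol 8.1.1 allows earlier scans if progression is suspected, and confirmatory scans from 4 weeks after the previous one (8 + 4 = week 12), so it can be sooner.

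**6. Weight of one patient.** Protocol 6.1.2 caps escalation cohorts at 6 (1/6 = 16.7 points of response rate) and allows up to 12 at the recommended dose (1/12 = 8.3 points).

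**7. Scans after subsequent therapy.** Protocol 8.1.1 continues scanning until confirmed progression even after new therapy, and SAP 3.2.2.1.1 continues after symptomatic progression where possible. Appendix H stops Combination Module 1 scans at treatment discontinuation, and stops all scans after symptomatic deterioration.

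**The case against.** The strongest reply is that little turns on this. Development was halted and the efficacy outputs are limited and meant for publication (SAP 1.1). The planned Part B interim analysis of response rate is no longer in the SAP. Response rate is descriptive, with 80% intervals. A conflict needs a missing lesion, a nadir below baseline, unequal shrinkage and a reading within a band 3.6 mm wide in each illustration, all with assumed sizes. This limits the weight, and it stands. It does not remove the undeclared difference.

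A second reply is that the protocol is not one clean comparator, because Appendix H Table 2 gives not evaluable where 9.4.1 scales. That also stands. A reader might infer that the baseline-versus-nadir conflict covers intervened lesions too. It does not: 9.4.1 has no scaling rule for them, and the SAP departs there from Table 2.

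A third reply concerns best percentage change. A reader might infer that the SAP dropped a protocol cut-off. The definition in protocol 9.4.1 has none, so there was nothing to depart from. Other anti-cancer therapy is prohibited during study treatment (protocol Table 5), so exposure arises essentially from off-treatment scans before progression, on which the documents disagree.

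**Conclusion.** The point holds within limits. For missing target lesions, protocol 9.4.1 and the SAP prescribe different references, Section 6 is silent, and identical scans can move between progression and partial response in either direction. For intervened lesions the SAP departs from the not-evaluable rule in Appendix H Table 2. The worked example is mislabelled, on the inference that its printed result follows the SAP's own rule. The missing cut-off for best percentage change is a gap shared with the protocol and worth closing.

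It would be tempting to conclude that the response results are biased. The documents do not support that: the illustrations run both ways, the lesion sizes are assumed, and the number of affected visits cannot be derived. All endpoints concerned are secondary and descriptive. The change should be made; nothing in the primary safety objective depends on it.

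**What to change.** Before database lock:

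- Keep one scaling reference, the nadir as the SAP states, for missing lesions, intervened lesions and the sums that set later nadirs. List it in SAP Section 6 as a departure from protocol 9.4.1 and from the not-evaluable rule in Appendix H Table 2.
- Reword the example to say that the nadir sum of lesions 1–5 was 29.3 cm, after checking that this was meant.
- In SAP 3.2.2.1.5 and 4.2.2, restrict best percentage change and the waterfall to assessments before any subsequent anti-cancer therapy, as defined for response rate in SAP 3.2.2.1.3 (which does not count radiotherapy). Note this in Section 6, since it narrows the open protocol definition.

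The cost is SAP text, the programming specification and Section 6 entries, with no new data. The protocol's two rules would still differ on paper, but the analysis rule would be settled and declared. The waterfall may look slightly less favourable.
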